#### **16.3.4. Protocol Amendments and Deviations**

If a clarification on a procedure or an error is found in the protocol, a protocol clarification memo will be sent to all sites and the IRB/IEC/REB before an amendment is issued.

Changes to the administrative aspects of the study (eg, changes in contact information or study personnel) will not require formal protocol amendments or IRB/IEC/REB approval but can be treated as administrative amendments. However, the IRB/IEC/REB should be kept informed of such changes.

Nonadministrative changes to the protocol, initiated either by Amicus or the investigator, will require a formal amendment procedure. Approval of all amendments must be obtained from Amicus, relevant IRB/IEC/REB, and regulatory authorities (in accordance with local requirements) prior to implementation.

Protocol deviations that may significantly impact subject safety or scientific integrity (eg, changes to eligibility criteria, addition or deletion of tests, dosing, duration of treatment, and/or other aspects of study design) are not permitted under GCP or by Amicus, unless necessary to eliminate an immediate hazard to the subject(s). Where Amicus and/or the investigator must take urgent safety measures to protect subjects from an immediate hazard, a protocol deviation may be allowed prior to obtaining approval from the relevant IRB/IEC/REB (and/or regulatory authorities) according to 21 Code of Federal Regulations 312.30(b) (2). In such cases, Amicus and the IRB/IEC/REB must be notified within 1 business day.

Amicus and the relevant IRB/IEC/REB, where required by local law, must be informed of all protocol deviations and violations, and the investigators shall document such protocol deviations and violations in subject source documents and eCRFs.

#### **16.3.5. Delegation of Investigator Duties**

The investigator should ensure that all persons assisting with this study are adequately qualified and informed about their study-related duties and functions, the protocol, any amendments to the protocol, and the study treatment.

Amicus will select a coordinating investigator as a representative of all investigators for this study. Each investigator must maintain a list of sub-investigators and other appropriately qualified persons to whom they delegate significant study-related duties.

Should the investigator delegate the supervision of the administration of the study drugs, the designee should have the appropriate medical qualifications to effectively conduct or supervise

any potential resuscitation procedures. Even if the investigator delegates any trial-related duties to other qualified members of his or her study staff, the investigator retains ultimate responsibility for obtaining informed consent from study subjects; for ensuring that the investigation is conducted according to the protocol, the signed investigator statement (Form FDA 1572 or Statement of Foreign Investigator), and applicable regulations; for protecting the rights, safety, and welfare of study subjects; and for the control of investigational products under evaluation.

#### **16.3.6. Study and Site Closure**

Upon completion or termination of the study, the Amicus monitor or its designee will conduct site closure activities with the investigator or site personnel (as appropriate), in accordance with applicable regulations, GCP, and standard operating procedures of Amicus or its designee.

Amicus reserves the right to temporarily suspend or terminate the study at any time for reasons including (but not limited to) safety issues, ethical issues, or severe noncompliance. If Amicus determines that such action is required, Amicus will discuss the reasons for taking such action with the investigator or head of the medical institution (where applicable). When feasible, Amicus will provide advance notice to the investigator or head of the medical institution of the impending action.

If a study is suspended or terminated for safety reasons, Amicus will promptly inform all investigators, heads of the medical institutions (where applicable), and/or institutions conducting the study. Amicus or its designee will also promptly inform the relevant regulatory authorities of the suspension/termination along with the reasons for such action. Where required by applicable regulations, the investigator or head of the medical institution must inform the IRB/IEC/REB promptly and provide the reason(s) for the suspension/termination.

### **16.4. Legal and Financial Aspects**

#### **16.4.1. Liability and Insurance**

Liability and insurance provisions for this study are provided in separate agreements.

#### **16.4.2. Financial Disclosure**

Before the start of the study, the investigator will disclose to Amicus any proprietary or financial interests he or she might hold in the investigational products, miglustat (as in Zavesca), Myozyme, Lumizyme, or Amicus, as outlined in the financial disclosure form provided by Amicus. The investigator agrees to update this information in case of significant changes during the study or within 1 year of its completion. The investigator also agrees that, where required by law or regulation, Amicus may submit this financial information to domestic or foreign regulatory authorities in applications for marketing authorizations.

Where required by regulation:

- The investigator will disclose his/her financial interests to the subjects in the informed consent information.
- The investigator or Amicus, on behalf of the investigator, will submit the financial arrangements for the study to the regulatory authorities or to the IRB/IEC/REB.

Each sub-investigator to whom the investigator delegates significant study-related responsibilities will provide financial disclosures.

## **16.5. Records Retention**

Following closure of the study, the investigator or head of the medical institution (where applicable) must maintain all site study records (except for those required by local regulations to be maintained elsewhere) in a safe and secure location. The records must be easily accessible when needed (eg, for a sponsor audit or regulatory inspection) and must be available for review in conjunction with assessment of the facility, supporting systems, and relevant site personnel.

Where permitted by local laws/regulations or institutional policy, some or all of the records may be maintained in a format other than hard copy (eg, microfiche, scanned, and electronic); however, caution must be exercised before such action is taken. The investigator must ensure that all reproductions are legible and are a true and accurate copy of the original. In addition, they must meet accessibility and retrieval standards, including regeneration of a hard copy, if required. The investigator must also ensure that an acceptable back-up of the reproductions exists and that there is an acceptable quality control procedure in place for creating the reproductions.

Amicus (or designee) will inform the investigator of the time period for retaining the site records in order to comply with all applicable regulatory requirements. The minimum retention time will meet the strictest standard applicable to a particular site, as dictated by local laws/regulations, Amicus' standard operating procedures, and/or institutional requirements.

The investigator must notify Amicus of any changes in the archival arrangements, including, but not limited to, archival of records at an off-site facility or transfer of ownership of the records in the event that the investigator is no longer associated with the site.

## **16.6. Use of Study Findings**

All information concerning the operation of Amicus that has been provided by Amicus and is unpublished is confidential and must remain the sole property of Amicus. The investigator agrees to use the information only for the purposes of carrying out this study and for no other purpose unless prior written permission from Amicus is obtained.

Amicus has full ownership of the data collected as part of the study.

By signing the clinical study protocol and the confidentiality agreement, the investigator agrees that the results of the study may be used for the purposes of national and international registration, publication, and information for medical and pharmaceutical professionals. The authorities will be notified of the investigator's name, address, qualifications, and extent of involvement.

Amicus will ensure that a final report on the study is prepared and will ensure that the study findings are reported in a manner that complies with applicable requirements for reporting clinical study results. The final analysis will be performed for the final CSR based on a data cutoff date of 31 December 2024. Any data collected after this date will be provided as an addendum to the final CSR when all subjects have completed the study or have been withdrawn from the study.

### 7. OBJECTIVE

The objective of this amendment is to continue collecting long-term safety and efficacy data on LOPD subjects treated with cipaglucosidase alfa/miglustat while decreasing some of the burden on those subjects taking part, and continuing to provide treatment where regulatory approval has not yet been granted or the product is not yet commercially available.

### 8. INVESTIGATIONAL PLAN

#### 8.1. Study Design

This is a multicenter, international, open-label extension study of cipaglucosidase alfa/miglustat in adult subjects with LOPD who completed Study ATB200-03. No additional subjects will be enrolled after data cutoff date of 31 December 2024.

Upon approval of this amendment, any subjects continuing in the study will follow the updated Schedule of Assessments in [Table 10](#).

Upon approval of this amendment, study visits that include minimal efficacy, safety, and other assessments will be scheduled approximately every 52 weeks. These visits may occur over 2 days, provided all study assessments and procedures are performed before administration of study drug. The relevant IRBs, ECs, and REBs should be notified of any deviations from the protocol.

Efficacy assessments (ie, functional assessments) include evaluation of ambulatory function (6MWT) and pulmonary function tests (FVC). Safety assessments include monitoring of AEs, including IARs, vital signs, physical examinations including weight. Concomitant medications and nondrug therapies will also be recorded.

The study will continue until one of the conditions outlined in Section [8.2](#) in the main body of the protocol is met.

### 9. SUBJECT SELECTION AND WITHDRAWAL CRITERIA

Please refer to Section [9](#) in the main body of the protocol.

### 10. TREATMENT OF SUBJECTS

Please refer to Section [10](#) in the main body of the protocol.

### 11. STUDY DRUG MATERIALS AND MANAGEMENT

Please refer to Section [11](#) in the main body of the protocol.

## **12. STUDY PARAMETERS AND PROCEDURES**

### **12.1. Schedule of Assessments**

A Schedule of Assessments showing each study assessment and procedure along with the scheduled time of occurrence is provided for subjects who continue in the study upon approval of this protocol amendment ([Table 10](#)).

All study assessments should be conducted by the investigator and/or a suitably qualified designee. Information will be recorded in the source documents and, where appropriate, in the eCRF.

Visits may occur over 2 days; if assessments are not able to be completed in 2 days, an additional day may be scheduled. Once established, every effort should be made to maintain the order of procedures, approximately at the same time of day, at each study visit throughout the study, regardless of the number of days that are used for the visit.

If an infusion (or infusions) were missed close to the scheduled assessments at any of the study visits, it should be communicated with the Amicus Medical Monitor to determine on a case by case basis whether catch-up infusions are needed and how many catch-up infusions are needed prior to the study assessments. The rationale for the missed infusion should be captured.

For additional details on study visits and description of study assessments, please refer to Section [12.2](#) and Section [12.3](#).

**Table 10: Schedule of Assessments for Subjects Who Continue Under Protocol Amendment 3**

Study Visit	Treatment			Follow-up ≥ 30 Days After Last Dose
	Infusion Visits (Every 2 Weeks Through EOS/ET)	Every 52 Weeks a	EOS/ET	
Visit Window (Days)	± 3	± 3	± 3	± 3
Schedule next visit	X	X	X	
Clinical Assessment				
Concomitant medications and nondrug therapies (12.3.3)	X	X	X	X
Complete PE b (12.3.4)		X	X	
Vital signs (12.3.6)	X	X	X	
Weight c (12.3.5)		X	X	
AEs/SAEs, including IARs (13)	X	X	X	X
12-lead ECG d (12.3.10)		X	X	
Serum chemistry, hematology d (12.3.11.1)		X	X	
Urine pregnancy test e (12.3.11.2)	X	X	X	
Pulmonary Function Tests				
FVC (sitting, supine) (12.3.16)		X	X	
Motor Function Assessments				
6MWT (12.3.18)		X	X	

**Table 10: Schedule of Assessments for Subjects Who Continue Under Protocol Amendment 3 (Continued)**

Study Visit	Treatment			Follow-up ≥ 30 Days After Last Dose
	Infusion Visits (Every 2 Weeks Through EOS/ET)	Every 52 Weeksa	EOS/ET	
Visit Window (Days)	± 3	± 3	± 3	± 3
Study Drug Administration				
Miglustat (10)	Every 2 weeks 1 hour before infusion of cipaglucosidase alfa			
Cipaglucosidase alfa (10)	Every 2 weeks			

Abbreviations: 6MWT = 6-minute walk test; AE = adverse event; ECG = electrocardiogram; EOS = end of study; ET = early termination; FVC = forced vital capacity; IRT = interactive response technology; PE = physical examination; SAE = serious adverse event

a Study visits will be scheduled every 52 weeks until study termination by the sponsor.

b Complete physical examinations will include assessment of head, ears, eyes, nose, throat (HEENT), respiratory, cardiovascular, lymphatic, gastrointestinal, and neurologic systems.

c Weight will be entered into the IRT system every 52 weeks for calculation of cipaglucosidase alfa dose.

d Test to be performed locally.

e Urine pregnancy tests are performed locally only for female subjects of childbearing potential. If the urine pregnancy test has a positive result, study drug will not be administered and a confirmatory serum pregnancy test will be performed.

## **13. ADVERSE EVENTS AND SERIOUS ADVERSE EVENTS**

Please refer to Section 13 in the main body of the protocol.

## **14. DATA MANAGEMENT**

Please refer to Section 14 in the main body of the protocol.

## **15. DATA ANALYSIS AND STATISTICAL CONSIDERATIONS**

### **15.1. Endpoints**

#### **15.1.1. Safety Endpoints**

The long-term safety profile of cipaglucosidase alfa/miglustat will be characterized using incidence of TEAEs, SAEs, and AEs leading to discontinuation of study drug, frequency and severity of immediate and late IARs, and any abnormalities noted in other safety assessments (eg, clinical laboratory tests, ECGs, vital signs). Immunogenicity to cipaglucosidase alfa will also be described.

#### **15.1.2. Efficacy Endpoints**

Efficacy measures are as follows:

- 6MWD
- 6MWD (% predicted)
- sitting FVC (% predicted)

### **15.2. Sample Size Considerations**

No formal sample size calculation was performed for this open-label extension study. The maximum sample size for this study is based on the number of subjects who complete Study ATB200-03, which has a target enrollment of 110 subjects.

### **15.3. Data Analysis Considerations**

The Statistical Analysis System (SAS®) version 9.4 (or latest version at the time of the analysis) and R® software will be used for all statistical procedures and analyses.

Full details of the data and analysis methods will be provided in the statistical analysis plan.

#### **15.3.1. Analysis Populations**

The open-label extension remaining safety (OLE-RS) population includes all subjects who remained in the open-label extension study ATB200-07 and continued to receive treatment under this amendment. The OLE-RS population will be used for all analyses (including safety and efficacy).

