## **8.4. Definition of the End of Study**

End of study is defined as the date of the last subject's last visit. The final analysis will be performed for the final CSR based on a data cutoff date of 31 December 2024. Any data collected after this date will be provided as an addendum to the final CSR when all subjects have completed the study or have been withdrawn from the study. Upon approval of this amendment, subjects who remain in the study will follow the Schedule of Assessments in [Appendix 1](#) ([Table 10](#)).

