For all subjects, AEs and SAEs will be reported from time of first dose of open-label study drug until 30 days after the last dose of study drug. If the investigator becomes aware of an SAE in a subject or receives an unsolicited report of an SAE from a subject more than 30 days after the last treatment, and considers the event possibly, probably, or definitely related to previous study treatment, he or she should contact the Amicus medical monitor to determine how the SAE should be documented and reported.

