### **15.3.2. Treatment Groups**

There will be a single treatment group to be analyzed following this amendment, and that is the subjects who remained in the OLE study under Protocol Amendment 3.

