## 1. INTRODUCTION

This statistical analysis plan (SAP) describes the planned data analyses and the outputs to be included in the final clinical study report (CSR) for the standalone open-label extension (OLE) Study ATB200-07. The SAP is based on Amendment 3 of the Protocol for Study ATB200-07 dated 10 December 2024.

This final SAP describes the analyses that will be performed for the final CSR for the standalone Study ATB200-07 based on a data cutoff date of 31 December 2024. All data collected through the cutoff date will be reported as summary tables and/or listings.

This SAP has been developed in accordance with Good Clinical Practice (GCP), International Council on Harmonisation (ICH) guideline E9 (Statistical Principles for Clinical Trials), and Amicus standard operating procedure (SOP) ATCRA-SOP-AT-008.

The analyses and statistical methods specified in the final SAP supersede those described in the study protocol.

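### The addendum's only analysis set (OLE-RS) omits post-cutoff safety data from subjects who leave before Amendment 3 is approved at their site, although the protocol promises all post-cutoff data in the addendum

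*Protocol*

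**What the plan says.** - **Final CSR.** SAP section 1 sets the boundary at 31 December 2024: "All data collected through the cutoff date will be reported as summary tables and/or listings". Its safety set (SAP 4.1.2) is everyone with at least one dose in ATB200-07.
- **Promise for later data.** Protocol 8.4 states: "Any data collected after this date will be provided as an addendum to the final CSR". Sections 15 and 16.6 repeat this. None of the three restricts it to a subset of subjects.
- **Addendum population.** Appendix 1, 15.3.1 defines one set, OLE-RS, which "includes all subjects who remained in the open-label extension study ATB200-07 and continued to receive treatment under this amendment", and assigns it to every analysis, safety as well as efficacy. Appendix 1, 15.3.2 names one treatment group, "that is the subjects who remained in the OLE study under Protocol Amendment 3". Appendix 1, 15.3.4.2 repeats OLE-RS for safety.
- **Addendum data start.** Appendix 1, 15.3.4 restricts all addendum analyses to data collected after database lock (DBL) for the final CSR, and excludes anything that existed before it.
- **When the amendment applies.** Protocol 8.1 and Appendix 1, 8.1: "Upon approval of this amendment, any subjects continuing in the study will follow the updated Schedule of Assessments". Section 16.3.4: "Approval of all amendments must be obtained from Amicus, relevant IRB/IEC/REB, and regulatory authorities (in accordance with local requirements) prior to implementation".
- **Safety reporting period.** Section 13.1.2: "AEs and SAEs will be reported from time of first dose of open-label study drug until 30 days after the last dose of study drug". SAP 7.2 uses the same 30-day limit for treatment-emergent events.

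**The concern.** Membership of OLE-RS depends on something that happens after the cutoff: the subject must still be in the study and on treatment once Amendment 3 is in force at the site. A subject who dies or stops for an adverse event before then can never qualify. In a study whose stated purpose is long-term safety, that selects on the outcome. The protocol's other safety sets require only one dose.

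At stake are the addendum's counts of deaths, SAEs and discontinuations due to AEs. Appendix 1, 15.3.4.2 plans summaries and listings of all three, but on a set that has already lost the earliest leavers. In an extension capped at about 110 subjects, a single unreported death or serious infusion reaction would matter.

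**Working it through.** There is no planned figure to reproduce, because the study has no formal sample size calculation. The check compares the definitions and then works through the dates.

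**1. Where each kind of post-cutoff event goes, as written**

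| Subject and event | Final CSR | Addendum |
|---|---|---|
| Continues under Amendment 3; event after DBL | Outside (after cutoff) | Included |
| Continues under Amendment 3; event between cutoff and DBL | Outside | In OLE-RS, but excluded by the data start in 15.3.4 |
| On drug at cutoff; dies, stops or transfers before site approval | Outside | Not in OLE-RS |
| Last dose in December 2024, before site approval; AE in January 2025 within 30 days | Outside | Not in OLE-RS |

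The last two rows are the present point. The second row is a separate defect in the same appendix, and it affects the remedy. A subject who leaves after dosing under the amendment can be read as included, although no minimum such as one dose is stated; such subjects are not counted here.

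**2. Dates**

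- Amendment 3 is dated 10 December 2024, 21 days before the cutoff. Approval dates are not given.
- 31 December minus 30 days is 1 December 2024. For any subject who stopped with a last dose on or after 2 December, part of the 30-day window falls after the cutoff. Example: a last dose on 15 December has a window ending on 14 January 2025, so 14 days lie beyond the cutoff.

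**3. Interaction with the lock date**

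Events between cutoff and DBL are already outside the addendum for everyone. As the text stands, the population rule therefore removes further events only when they occur after DBL in someone who left before site approval. Once the data start is moved to the cutoff, the population rule becomes the only barrier and removes all post-cutoff events in such subjects. Neither change alone recovers these data.

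**4. Illustration of size (every input assumed)**

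Let n be the subjects on treatment at the cutoff, r the yearly rate of exits of all kinds, and m the months from cutoff to site approval. Then p = 1 − exp(−r·m/12), expected exits = n·p, and P(at least one) = 1 − (1 − p)^n.

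| n | r | m | p | Expected exits | P(at least one) |
|---|---|---|---|---|---|
| 30 | 2% | 1 | 0.0017 | 0.05 | 0.05 |
| 60 | 5% | 3 | 0.0124 | 0.75 | 0.53 |
| 60 | 5% | 6 | 0.0247 | 1.48 | 0.78 |
| 110 | 10% | 12 | 0.0952 | 10.5 | about 1.00 |

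These are exits for any reason, not deaths or AE withdrawals. The first and last rows are the ends of the grid tried.

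**The case against.** The strongest replies, and what stands of each:

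- **These subjects are not lost from the study report.** A reader might infer that they appear in neither report. The documents do not support that. Anyone dosed in ATB200-07 is in the OLE safety population (SAP 4.1.2) and in the disposition table (SAP 5.1), with data through the cutoff. Only their later data are affected. This stands fully.
- **The main long-term safety analysis is untouched.** Protocol section 7 ties the listed objectives to the final CSR at the cutoff. The objective in Appendix 1 is continued collection of safety and efficacy data, reported descriptively. This stands; the bias concerns the addendum only.
- **Exits may be administrative.** Section 8.2 ends treatment on commercial availability or post-trial access, section 8.5 counts such subjects as completers, and section 6.1 says the product is already approved in several regions. This stands, and it limits any claim about size. A reader might try to express the loss as a share of post-cutoff exits. At low exit rates that share is roughly the lag divided by the follow-up (2/24 = 8%, 9/12 = 75%), so it mainly restates whichever lag is assumed. It also says nothing about how many exits are adverse outcomes.
- **An addendum SAP could still list these data.** The supplied SAP covers only the final CSR, and the protocol defers details to a SAP. Section 8.4 could be met by listings outside OLE-RS. So non-reporting is not shown. But Appendix 1 assigns all analyses to OLE-RS, and a later SAP would have to depart from that text.
- **SAP 3.1 mentions a 30-day safety follow-up.** It does so, but nothing there extends the data boundary in SAP section 1.

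**Conclusion.** The protocol contradicts itself. Three sections promise all post-cutoff data in the addendum, while Appendix 1 confines every addendum analysis to subjects treated under Amendment 3. This is a stated rule and not an omitted detail. Subjects on drug, or within 30 days of their last dose, at the cutoff who leave before site approval have post-cutoff AEs, SAEs, deaths and EOS/ET data in no defined analysis.

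The direction is favourable to the drug to the extent that those exits are deaths or AE withdrawals. The magnitude is not derivable: the number still on treatment, approval dates, lock date, exit rates and the mix of exit reasons are all absent. The illustration allows anything from practically none to about ten exits. A claim of large bias, or of damage to the final CSR's safety conclusions, would go beyond the documents.

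**What to change.** 1. In Appendix 1, 15.3.1, define the addendum safety population as all OLE safety population subjects who on 31 December 2024 were on study drug or within 30 days of their last dose, whether or not they continued under Amendment 3. Use it for AE, SAE, death, discontinuation and disposition outputs.
2. Align the treatment group in Appendix 1, 15.3.2 and the safety population in 15.3.4.2 with that definition.
3. In Appendix 1, 15.3.4, and in the matching post-lock wording of 15.3.4.1.1 and 15.3.4.2, move the data start from DBL to the day after the 31 December 2024 cutoff. Step 1 without this step would still lose events between cutoff and lock.
4. Keep OLE-RS for the 52-week visit-based summaries, and list the EOS/ET values of earlier leavers beside them.

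Cost: text changes in several subsections of Appendix 1, carried into the addendum SAP. No new data are needed, because until site approval subjects remain on Table 4, which already schedules AE collection, the EOS/ET visit and follow-up. The downside is that a few subjects with short post-cutoff follow-up enter the safety denominator.
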